5.4 Demographics and Baseline Characteristics

Demographics and baseline characteristics will be summarised by treatment group for the ITT and PP populations. Continuous variables will be tested with Mann-Whitney U-test between the two groups, dichotomous variables with Fishers exact test, ordered categorical variables with Mantel-Haenszel Chi-square test and non-ordered categorical variables with Chi-square test. Site and country will not be tested between treatments.

5.5 Medical and Surgical History

Medical and surgical history will be summarized by System Organ Class (SOC) and Preferred Term (PT) for each treatment group for the ITT population. No statistical testing will be done.

5.6 Prior and Concomitant Medications

Prior and concomitant medication will be summarised by higher level anatomical therapeutic classification (ATC) group and generic term for each treatment group for ITT population. No statistical testing will be done.

5.7 Efficacy Analyses

5.7.1 Primary Efficacy Analysis

5.7.1.1. Clinical analysis

The combined primary variable will be analysed by the Mantel-Haenszel Chi-square test. The variable will be summarised in a table as a categorical variable. A stacked bar chart (up to

STATISTISKA KONSULTGRUPPEN		Statistical Analysis Plan	
Protocol: Clinical and health economic evaluation with a new Baha abutment design combined with a minimally invasive surgical technique		Protocol No: CBAS5439	
		Version: 1.0	Page 17 of 23

100%) with one bar per treatment group will be produced. A plot of individual values of Holgers Index, Overgrowth, Pain (scar/neuropathic) according to POSAS or pain questions in CRF and Numbness with patient number on the y-axis and time (3 weeks to 1 year) on x-axis. The individual values will be shown as different symbols at each visit to indicate level of complication.

5.7.1.2. Cost analysis

The mean total costs per group will be presented and the difference analyzed using a t-test, if the data is normally distributed. In case of skewed data bootstrapped 95% CI will be presented. Medians will be presented, and the difference will be tested using the Mann-Whitney U test.

5.7.2 Secondary Efficacy Analyses

The combined variable used in the primary analysis will also be analysed in the same way but for PP population and also only for subjects who completed all visits in the study.

The distribution of Holgers Index will be tested between treatment groups with Mantel-Haenszel Chi-square test at each visit. Holgers index by visit will also be presented in a figure. Max of Holgers Index per patient will be tested in the same way but only once and not per visit. The distribution of all Holgers Index values over all visits will be presented but no testing of this will be done.

Holgers Index according to AE reporting will be analysed by:

- Plot the incidence rate Holgers ≥ 2 per day over time
- Plot individual patient Holgers Index values using boxes/bars indicated by different colours by severity with patients on y-axis and calendar time on x-axis.
- The distribution of all Holgers Index values over all AEs will be presented by treatment group but no testing of this will be done.
- Plot visit Holgers data and movement between visits by treatment group.

The distribution of soft tissue thickening/overgrowth will be tested between treatment groups with Mantel-Haenszel Chi-square test at each visit.

The number of resources and costs of the components Direct medical costs will be summarised by treatment groups. The costs of the 3 components: surgery, wound dressing and complications will be tested between groups by using Mann-Whitney U test.

Wound healing will be tested between treatment groups by visit with Fishers exact test.

The visible abutment length and change from visit 3 will be tested between groups by visit by using Mann-Whitney U test. This test will only be done for patients with no change of abutment. For patients with an abutment change spaghetti plots will be created of the visual abutment length over time with indication of when abutment change is made and an indication of length of the new abutment.

The aesthetic outcome (POSAS) scales and the two pain questions will be tested between groups by visit by using Mann-Whitney U test.

The distribution of numbness will be tested between treatment groups with Mantel-Haenszel Chi-square test at each visit.

Surgery time will be tested between groups by using Mann-Whitney U test.

STATISTISKA KONSULTGRUPPEN		Statistical Analysis Plan	
Protocol: Clinical and health economic evaluation with a new Baha abutment design combined with a minimally invasive surgical technique		Protocol No: CBAS5439	
		Version: 1.0	Page 18 of 23

5.7.3 Tertiary Efficacy Analyses

Holgers Index according to AE reporting will be analysed by:

- Plot the mean Holgers Index per day and treatment group

Health Utilities Index (HUI-III) dimensions and overall score will be tested between groups by using Mann-Whitney U test by visit. The Health Utilities Index (HUI-III) QALY will be tested between groups by using Mann-Whitney U test.

APHAB will be tested between groups by using Mann-Whitney U test by visit. The APHAB global score AUC will be tested between groups by using Mann-Whitney U test.

Use of sound processor will be calculated for those who used a processor. Number of hours per week will be tested between groups by using Mann-Whitney U test by visit. Type of sound processor used at a visit will be presented with number and percentage (no statistical testing).

Absolute ISQ High and Low values will be presented by visit and abutment length. Patients can change abutment length during the study. Change in ISQ High and ISQ Low and AUC analysis will be made by visit for all patients and also for patients without change of abutment length during the study. Test between groups will be performed using Mann-Whitney U-test.

Smoking habits (No, Smoking - Less than 10 cigarettes/day, Smoking - Between 11 and 20 cigarettes/day, Smoking - Between 21 and 40 cigarettes/day, Smoking - More than 40 cigarettes/day) will be presented by visit and between groups will be performed using Mantel-Haenszel Chi-square test at each visit.

Type of surgery will be tested between groups using Fishers exact test.

Skin thickness (test group only) will only be described descriptively.

Length of the abutment will be described with frequencies between groups. No statistical testing will be done.

Cost consequence analysis between treatment groups will be made. HUI-III (QALY), APHAB, POSAS and Holgers Index AUC will be used together with the total cost. Estimates per treatment group and for the difference between groups with 95% CI will be presented. Additional analyses per SSD, Conductive and Mixed and per country and site will be presented.

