6.4 Baha sound processor installation

A Baha sound processor will be installed to the implant at visit 4 (i.e. 3 weeks after surgery). If the wound is not considered sufficiently healed, as judged by the surgeon/surgical nurse, the installation shall be delayed to a scheduled subsequent visit or extra visit, when the site is considered sufficiently healed.

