9.4 General statistical methodology

For comparison between the two study groups the Mantel-Haenszel chi-square test will be used for ordered categorical variables, the Mann-Whitney U-test for continuous variables, Fisher's exact test for dichotomous variables and the Chi-square test for non-ordered categorical variables.

The distribution of continuous variables will be given as n, mean, SD, Median, Min and Max and the distribution of dichotomous and categorical variables will be given as number and percentages.

The main analyses will be performed on the ITT population and complementary analyses will be performed on the PP population.

The main analyses will be performed unadjusted. If significant statistical differences in demographics and baseline variables are found, complementary analyses will be performed adjusted for these variables.

The main analysis will be after 12 months of follow-up and repeated after 3 years. All statistical tests will be two-sided.

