4.2.5.6. Variables for the cost consequence analysis

- HUI-III utility scores will be calculated before surgery, at 24 weeks, at 12 months after surgery. The HUI-III QALY over 1 year will be calculated using the following AUC method: multiplying the average utility of two subsequent measurements with the time interval, and adding up over both time intervals. In case of missing values prior to surgery, the mean of patients with a similar aetiology (SSD, mixed, conductive) will be used. In case of a missing value at 6 months, this will be interpolated with the 1 year value. In case of a missing value at 1 year, the last observation carry forward (LOCF) technique will be used. In case of extra measurements, these will be added to the AUC calculation. In case of an implant and/or permanent abutment extrusion or removal, the last unaided HUI-III will be used to portray the last health state without the Baha, unless an extra HUI-III was performed to portray this health state.
- The unaided Global APHAB score before surgery and afterwards aided global APHAB score over the first year (AUC) will be calculated per patient. In case of

Protocol:

Clinical and health economic evaluation with a new Baha abutment design combined with a minimally invasive surgical technique

Protocol No:

CBAS5439

Version:

1.0

Page 15 of
23

missing values prior to surgery, the mean of patients with a similar aetiology (SSD, mixed, conductive) will be used. In case of a missing value at 6 months, this will be interpolated with the 1 year value. In case of a missing value at 1 year, the LOCF technique will be used. In case of extra measurements, these will be added to the AUC calculation. In case of an implant and/or permanent extrusion or abutment removal, the last unaided APHAB global score will be used.

- The POSAS before surgery can be presumed to be the lowest value (1) and afterwards the POSAS over the first year (AUC) will be calculated per patient. Same imputation rules as in APHAB and HUI-III will be made here.

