- The course of adverse soft tissue reactions will be calculated over the first year (AUC) per patient as measured by the Holgers Index taken from AE page and from visits. The Holgers index will be carried forward up to next change of Holgers index (at an ordinary visit or an extra visit due to an AE with Holgers). AUC ($y = \text{Holgers severity (0-4)}$, $x = \text{day 0 - 365}$). If no stop date for an AE with Holgers Index is entered, the AE is ongoing and should be counted from the start date and onwards. Sensitivity analyses of the carry forward for of Holgers from visits and onward will be made as required.

The AUC of the APHAB and HUI-3 will be calculated using the assumption that the health state before and after surgery is similar until the audiological fitting occurred with the Baha. The individual Baha fitting time will be used to compensate for the variability in centers. After fitting the average will be calculated between this time point and 4 weeks later (which will be imputed with the value of 24 weeks). The time point between 24 weeks and 1 year will also be averaged. This accumulates to the AUC of the first year.

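### The first-year QALY and APHAB AUC comparisons leave out the pre-randomisation score of the same instrument; adjusting for it would sharpen a tertiary analysis at no data cost

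*SAP*

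**What the plan says.** Protocol 7.3.9 and 7.3.10 have subjects complete HUI3 and APHAB at visit 1. Protocol 4.3 places randomisation at visit 2, the day of surgery, stratified by site. A pre-randomisation score is therefore planned for both instruments.

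SAP 4.2.5.6 builds that score into the first-year summaries. For the QALY, "HUI-III utility scores will be calculated before surgery, at 24 weeks, at 12 months after surgery", and the area is found by "multiplying the average utility of two subsequent measurements with the time interval, and adding up over both time intervals". The end of the same section adds another rule for the APHAB and HUI AUCs. It assumes that "the health state before and after surgery is similar until the audiological fitting occurred with the Baha", and then uses the individual fitting date.

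SAP 5.7.3 gives the comparisons: "The Health Utilities Index (HUI-III) QALY will be tested between groups by using Mann-Whitney U test" and "The APHAB global score AUC will be tested between groups by using Mann-Whitney U test". For the cost-consequence table, "Estimates per treatment group and for the difference between groups with 95% CI will be presented". No covariate is named in any of the three, and no method is named for the interval.

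Protocol 9.4 says "The main analyses will be performed unadjusted". It provides a complementary adjusted analysis only for baseline variables found to differ significantly between arms. Visit-1 HUI and APHAB are in neither list of baseline variables (Protocol 5.2.5, SAP 4.1.1), and the SAP does not repeat the rule.

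**The concern.** The visit-1 score affects the AUC in two ways: it carries its own weight in the area, and it predicts the 24-week and 12-month scores that carry the rest. With about 50 subjects per arm, a moderate chance difference in pre-operative utility is common, and an unadjusted arm difference passes part of it on to the QALY result. The interval is also wider than the collected data require.

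At stake is the tertiary cost-consequence table, where the QALY and APHAB differences stand beside total cost. There the estimate and its interval matter more than a p-value. The Protocol 9.4 rule would not help: it waits for a significant imbalance, is only complementary, and does not list these scores.

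**Working it through.** **The plan's own figures.** The documents state no power or precision for the QALY or the APHAB AUC. The sample-size figure is for the combined primary endpoint. Simulating the stated event distributions (40,000 trials, Mantel-Haenszel test at 0.0499) gives 80.4% power at 50 per group, against the stated 80%. Also 50/0.95 = 52.6, rounded up to the stated 53. I use 50 per arm below.

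**Weights on visit 1, week 24 and month 12, from SAP 4.2.5.6**
- Trapezoid, intervals of 24 and 28 weeks: 12/52, 26/52, 14/52 = 0.231, 0.500, 0.269.
- Fitting-date rule, with fitting at week 3 (Protocol 6.4): baseline held for 3 weeks, averaged with the week-24 value for 4 weeks, then the week-24 value held to week 24 (my reading), then the average of the last two scores. This gives 5/52, 33/52, 14/52 = 0.096, 0.635, 0.269.

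**Assumptions, not in the documents.** Utility SD 0.25 at each time; correlation r between baseline and each follow-up from 0.3 to 0.7; correlation f between the two follow-ups from 0.6 to 0.8.

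**Formulas**, with weights w0, w1, w2:
- v = w0² + w1² + w2² + 2·r·w0·(w1 + w2) + 2·f·w1·w2
- slope of AUC on baseline: b = w0 + r·(w1 + w2)
- share of variance removed by adjustment: R² = b²/v
- unadjusted SE of the arm difference: 0.25·√(2v/50); adjusted SE: that × √(1 − R²)

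**Worked case**, trapezoid, r = 0.3, f = 0.7: b = 0.231 + 0.3 × 0.769 = 0.462 and v = 0.671, so R² = 0.213/0.671 = 0.32. The SE is 0.25 × √(2 × 0.671/50) = 0.041, and adjusted 0.041 × √0.68 = 0.034.

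The last column is the shift in the unadjusted QALY difference from a baseline imbalance of one standard error, 0.25 × √(2/50) = 0.05. It equals 0.05·b.

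| AUC rule | r | f | Variance removed | SE unadjusted | SE adjusted | Shift |
|---|---|---|---|---|---|---|
| Trapezoid | 0.3 | 0.7 | 32% | 0.041 | 0.034 | 0.023 |
| Trapezoid | 0.4 | 0.6 | 43% | 0.041 | 0.031 | 0.027 |
| Trapezoid | 0.5 | 0.7 | 51% | 0.043 | 0.030 | 0.031 |
| Trapezoid | 0.7 | 0.8 | 70% | 0.046 | 0.025 | 0.038 |
| Fitting date | 0.3 | 0.7 | 17% | 0.044 | 0.040 | 0.018 |
| Fitting date | 0.4 | 0.6 | 28% | 0.044 | 0.037 | 0.023 |
| Fitting date | 0.5 | 0.7 | 37% | 0.045 | 0.036 | 0.027 |
| Fitting date | 0.7 | 0.8 | 60% | 0.047 | 0.030 | 0.036 |

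With r = 0.7 and f = 0.7 the trapezoid figure is 73%, so the upper end depends slightly on f.

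**Where the shift comes from.** The direct weight contributes only 0.05 × 0.231 = 0.012 (trapezoid) or 0.05 × 0.096 = 0.005 (fitting date). The rest comes from the assumed correlation with follow-up.

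**Validity check.** I simulated no treatment effect (4,000 trials per setting, 50 per arm, r = 0.3, 0.5, 0.7, f = 0.7, both rules). Mann-Whitney rejected in 4.6% to 5.3% of trials overall. A baseline imbalance above 0.2 SD, in either direction, is expected in 32% of trials. Within those trials Mann-Whitney rejected in 7% to 13%, and regression on arm and baseline in 5% to 6%.

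**The case against.** The planned test is not an error. Randomisation makes the unadjusted comparison valid, and a correct 95% CI already allows for chance imbalance. A reader might infer that the plan inflates the false-positive rate or biases the QALY result. The documents do not support that: overall rejection under no effect stays near 5%. The higher rate appears only in trials that happen to be imbalanced. This part of the objection stands.

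A reader might also infer that the plan disregards baseline. It does not. Baseline is inside both AUCs. SAP 4.2.5 defines HUI change from visit 1, and SAP 4.2.5.1 defines aided APHAB minus the visit-1 unaided score. HUI is also scored at visit 1 and tested by visit, so an imbalance should be visible. These variables weaken any case for changing the by-visit analyses. They do not adjust the AUCs, so the point remains for those.

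The analyses are tertiary. Protocol 1.3.4 asks whether quality of life improves on receiving a Baha, which is a before/after question, and the primary economic endpoint is cost alone. No decision rule or power claim rests on the QALY. This stands and sets the priority.

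The size rests wholly on assumed values, and the APHAB gain is not quantified. Its baseline is unaided and its follow-up aided, so the correlation may be weak. This stands too. Unadjusted rank tests are also the protocol's general approach, applied consistently, but that is no reason to leave out a covariate that is already collected.

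**Conclusion.** The point holds as a missed gain in precision and a sensitivity to chance baseline imbalance in two tertiary AUC comparisons and the cost-consequence differences built on them. It does not reach either primary conclusion and does not make the planned tests invalid.

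Under the stated assumptions, adjustment removes about 17% to 70% of the variance of the QALY difference. A one-standard-error baseline imbalance moves the unadjusted difference by 0.018 to 0.038. It would be too strong to say that imbalance enters mainly through the direct weight, which is only 0.10 to 0.23; most of the shift follows from the assumed correlation. For APHAB the direction is the same, but the size is unknown and may be smaller.

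Label: free improvement. Priority: optional, tertiary analysis.

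**What to change.** In SAP 5.7.3, estimate the arm difference in HUI-III QALY and in APHAB global AUC by linear regression on arm, the visit-1 score of the same instrument, and site (the stratification factor), with a bootstrap 95% CI. Use these adjusted differences in the cost-consequence table; this also supplies the interval method that is now missing. Keep Mann-Whitney as a supportive test.

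In SAP 4.2.5.6, state which AUC rule defines each outcome, the plain trapezoid or the fitting-date rule, because they weight baseline differently. Where a visit-1 score is missing, the aetiology-mean imputation already planned there can supply the covariate; say that the mean is taken over both arms together.

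The by-visit analyses can stay as they are. The cost is SAP wording and a few lines of code, with no new data.

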5.7.4 Exploratory Clinical Efficacy Analyses

The following exploratory clinical efficacy variables will be *considered* for analysis. In case an analysis is performed, the results will be presented.

5.7.4.1. Holgers Index

The course of peri-abutment dermatitis will be calculated over the first year (AUC) per patient as measured in the Holgers Index taken from AE page and from visits for both groups. The AUC will be created by a predefined set of assumptions and rules. A sensitivity analysis will be conducted to assess the impact of these assumptions (worst/best case scaling).

STATISTISKA KONSULTGRUPPEN		Statistical Analysis Plan	
Protocol: Clinical and health economic evaluation with a new Baha abutment design combined with a minimally invasive surgical technique		Protocol No: CBAS5439	
		Version: 1.0	Page 19 of 23

5.7.4.2. Skin thickness/overgrowth

It is assumed that skin overgrowth is related to peri-abutment dermatitis. This would lead to a relation between the AUC of peri-abutment dermatitis and the skin thickness/overgrowth scale.

5.7.4.3. Pain

The area under the curve will be calculated for both groups of both pain attributes. This variable will be used in mixed models for hypothesis generating purposes.

5.7.4.4. Numbness

A mixed model will be created to investigate if numbness is related to pain for hypothesis generating purposes.

5.7.4.5. Aesthetic outcomes

The POSAS has been used in this study, but for Baha, no clinically relevant thresholds have been defined. An exploratory analysis using cluster analysis will be used to estimate the most clinically relevant thresholds and dimensions for the patient and observer outcomes.

5.7.4.6. Implant stability (ISQ)

A mixed model and/or cluster analyses will be performed for the different abutment types and lengths to determine what the normal clinical course of ISQ development is after surgery. This will possibly result in clinically relevant ISQ values.

5.7.4.7. Implant extrusion

Implant extrusion is clinically not expected to occur at random. We clinically can define two important periods, the period of osseointegration (up to three months) and the time after this period. Using a modelling approach, the incidence densities for implant extrusion will be calculated within these two period for hypothesis generating purposes.

5.7.4.8. APHAB

The mean benefits for the subscales will be presented together with the corresponding normalized percentiles for both the unaided and aided scores for both groups for hypothesis generating purposes. Also it will be investigated if a response shift is present during the first year.

5.7.4.9. Type of surgery

For the control group, two separate techniques (c-shape/linear) can be used. The relative amounts will be expressed.

5.7.4.10. Smoking

Smoking habits (No, Smoking - Less than 10 cigarettes/day, Smoking - Between 11 and 20 cigarettes/day, Smoking - Between 21 and 40 cigarettes/day, Smoking - More than 40 cigarettes/day) at visits 1, 4, 6, 8, 9 and 10. For hypothesis generating purposes, a mixed model will be created using the primary outcome and smoking as measured during this study in the first year.

STATISTISKA KONSULTGRUPPEN		Statistical Analysis Plan	
Protocol: Clinical and health economic evaluation with a new Baha abutment design combined with a minimally invasive surgical technique		Protocol No: CBAS5439	
		Version: 1.0	Page 20 of 23

5.7.4.11. *Per site analyses*

Any previous specified analyses may be performed per site.

5.8 Safety Analyses

5.8.1 *Loss of implant*

The loss of implants will be analysed with the Log-rank test between the two treatment groups and illustrated with Kaplan-Meier survival curves. The survival probabilities at 90 days, 180 days and at 365 days (from the KM-estimates) will be tabulated. Cox proportional Hazard ratio (with 95% CI) of implant loss for treatment group will be presented. Number of loss of implant and total follow up time per treatment group will be presented. Based on these numbers simulations (Markov-Modelling) of different scenarios will be made.

5.8.2 *Adverse Events*

Only treatment-emergent AEs will be included in the summaries for safety population.

A summary of subjects reporting at least one of the following AEs will be presented in an overview table:

- Any AE
- Any SAE
- Any treatment-related AE (Probably + Definitely)
- Any treatment-related SAE (Probably + Definitely)
- Death

Summaries per System Organ Class (SOC) and Preferred Term (PT) presenting n of AEs and n (%) of subjects with at least one AE will be provided for:

- All AEs (includes all serious and non-serious AEs)
- All AEs by Severity
- All AEs by Relation to Treatment
- All SAEs

5.8.3 *Device deficiency*

Number of Device Deficiencies and number and percentage of patients with a Device Deficiency.

5.8.4 *Removal of abutment*

Number and percentage of removal of abutment will be presented by treatment group.

